6.6.2 Clinical Laboratory Assessments

6.6.2.1 Potentially Clinically Significant Criteria

Any laboratory abnormalities deemed clinically significant by the investigator must be reported as an AE. A clinically significant abnormality is a confirmed abnormality (by repeat testing) that is changed sufficiently from Baseline so that in the judgment of the investigator a change in management is warranted. Any laboratory test showing abnormal results (including those recorded as AEs) that are believed to be possibly/probably related to study drug treatment will be repeated weekly (or as often as deemed prudent by the investigator) until the abnormality is resolved, returns to Baseline, or is otherwise explained. Laboratory assessments values meeting *any* of the following PCS low or PCS high criteria will be categorized as PCS:

Table 6-7 Clinical Laboratory PCS Criteria

Category	Parameter	SI Unit	PCS Criteria	
			PCS Low	PCS High
Chemistry	Albumin	g/L	< 0.9 × LLN	> 1.1 × ULN
	Alanine aminotransferase	U/L	—	≥ 3.0 × ULN
	Alkaline phosphatase	U/L	—	≥ 2.0 × ULN
	Aspartate aminotransferase	U/L	—	≥ 3.0 × ULN
	Bilirubin, total or direct	μmol/L	—	> 1.5 × ULN
	Calcium	mmol/L	< 0.9 × LLN	> 1.1 × ULN
	Chloride	mmol/L	< 0.9 × LLN	> 1.1 × ULN
	Cholesterol	mmol/L	—	> 1.3 × ULN
	Creatinine	μmol/L	—	> 1.3 × ULN
	Glucose, fasting	mmol/L	< 0.8 × LLN	> 1.2 × ULN
	Glucose, nonfasting	mmol/L	< 0.8 × LLN	> 1.4 × ULN
	Potassium	mmol/L	< 0.9 × LLN	> 1.1 × ULN
	Protein, total	g/L	< 0.9 × LLN	> 1.1 × ULN
	Sodium	mmol/L	< 0.9 × LLN	> 1.1 × ULN
	Triglycerides	mmol/L	—	> 2.0 × ULN
	Urea nitrogen	mmol/L	—	> 1.2 × ULN
Uric acid	μmol/L	—	> 1.2 × ULN	
Hematology	Basophils, absolute cell count	10 ⁹ /L	—	> 3.0 × ULN
	Neutrophils, absolute cell count	10 ⁹ /L	< 0.8 × LLN	> 1.5 × ULN
	Hematocrit	Ratio	< 0.9 × LLN	> 1.1 × ULN
	Hemoglobin	g/L	< 0.9 × LLN	> 1.1 × ULN
	Platelet count	10 ⁹ /L	≤ 0.5 × LLN	≥ 1.5 × ULN
	Red blood cell count	10 ¹² /L	< 0.9 × LLN	> 1.1 × ULN
	White blood cell count	10 ⁹ /L	≤ 0.7 × LLN	≥ 1.5 × ULN
Urinalysis	pH	—	< 0.9 × LLN	> 1.1 × ULN
	Specific gravity	—	—	> 1.1 × ULN

LLN = lower limit of normal value; ULN = upper limit of normal value; normal value provided by laboratory.

SI = Le Système International d'Unités (International System of Units).

6.6.2.2 Continuous Descriptive Parameters

The following laboratory parameters will be summarized:

Table 6-8 Clinical Descriptive Parameters

Category	Parameters
Hematology	
Hematocrit, Hemoglobin, Mean corpuscular hemoglobin (MCH), Mean corpuscular hemoglobin concentration (MCHC), Mean corpuscular volume (MCV), Platelet count, Red blood cell distribution width (RDW), Red blood cell count, White blood cell count, White blood cell differential (absolute counts only): Basophils, Eosinophils, Lymphocytes, Monocytes, Neutrophils
 
Part 1: Every visit Part 2: Subjects continuing from Part 1: every 6 months through the end of the study Newly enrolled subjects: Screening, Baseline, Months 1, 6, and 12 and every 6 months thereafter through the end of the study

Chemistry	
Alkaline phosphatase (ALP), Alanine aminotransferase (ALT), Albumin, Aspartate aminotransferase (AST), Direct bilirubin, Gamma-glutamyl transferase (GGT), Total bilirubin, Amylase (reflex lipase if amylase $\geq 1.5 \times$ ULN), Bicarbonate, Blood urea nitrogen (BUN), Calcium, Chloride, Cholesterol (total), Creatine phosphokinase (CPK), Creatinine, Glucose International normalized ratio (INR), Lactate dehydrogenase (LDH), Magnesium, Phosphorus, Potassium, Sodium, Total protein, Triglycerides, Uric acid
 
Part 1: Every visit Part 2: Subjects continuing from Part 1: every 6 months through the end of the study Newly randomized subjects: Screening, Baseline, Months 1, 6, and 12 and every 6 months thereafter through the end of the study

Serum Hepatic Fibrosis Indices	
Fibrosis 4 Score (FIB-4): Platelets, ALT, AST, Subject age Aspartate aminotransferase-to-platelet-count ratio (APRI): AST to platelet count ratio index, NAFLD Fibrosis Score (NFS): Subject age, BMI, AST, ALT, Platelets, Albumin ELF score: Subject age, BMI, AST, ALT, Platelets, Albumin PRO-C3
 
Part 1: Baseline, Months 6, and 12 Part 2: Subjects continuing from Part 1: every 12 months through end of study Newly randomized subjects: Screening, Baseline, Months 6 and 12, and every 12 months through end of study

Fasting Metabolic Parameters	
The following parameters may be included, but are not limited to: Lipid panel: Cholesterol (total), High density lipoprotein (HDL), Low density lipoprotein (LDL), Triglycerides, Very low-density lipoprotein (VLDL), Glucose, Insulin, Hemoglobin A1c (HbA1c)
 
Part 1: Baseline, Months 3, 6, and 12 Part 2: Subjects continuing from Part 1: every 6 months through the end of the study Newly randomized subjects: Baseline, every 6 months through the end of the Study

Biomarkers	
The following parameters may be included, but are not limited to: Fibrinogen, High-sensitivity C-reactive protein (hs-CRP), Interleukin (IL)-1β, IL-6
 
Part 1: Baseline, Months 3, 6, and 12 Part 2: Subjects continuing from Part 1: every 6 months through the end of the study Newly randomized subjects: Baseline, every 6 months through the end of the Study

Category	Parameters
Other Tests: Part 1 and Part 2	
Screening only: Ferritin, Follicle-stimulating hormone, (FSH) for postmenopausal women only Hemoglobin A1c (HbA1c), Hepatitis B surface antigen (HBsAg), Hepatitis C virus antibody (HCVAb), HCV RNA (only if HCVAb positive), HIV-1 and -2 antibodies
 
Screening, Month 12 and annually thereafter: α-fetoprotein (AFP)
 
All visits Urine pregnancy test for females of childbearing potential only. Positive urine pregnancy tests will be confirmed with a serum test.

Hepatic Panel Testing	
Part 1 and Part 2: Baseline and Unscheduled Visits
 
The following parameters may be included, but are not limited to:
 
Baseline only Anti-liver cytosol type 1 (anti-LC1), Antinuclear antibody (ANA), Anti-liver/kidney microsome type 1 (anti-LKM1) antibodies, Anti-smooth muscle antibodies (anti-SMA), Immunoglobulin G (IgG), Hepatitis B core antibody (HBcAb), Hepatitis B surface antibody (HBsAb) titer
 
Unscheduled Visits Antimitochondrial antibodies (AMA), ANA, Anti-LKM-1 type antibodies, anti-LC1 antibodies, Hepatitis A virus immunoglobulin M (HAV-Ab IgM), Hepatitis B virus surface antigen (HBsAg), Hepatitis C virus antibody (HCVAb), Hepatitis D virus antibody, Hepatitis E virus RNA by PCR, Immunoglobulin G subclass 1, anti-SMA, Alkaline phosphatase (ALP), Alanine aminotransferase (ALT), Aspartate aminotransferase (AST), Direct bilirubin, Total bilirubin

6.6.2.3 Character Values

Character values (e.g., < 5, negative) will be reviewed prior to database lock and converted to numeric values for analysis as appropriate. These conversions will be documented in the ADaM specifications.

6.6.3 Vital Signs

6.6.3.1 Potentially Clinically Significant Criteria

For vital signs, the PCS criteria are for weight change, as shown below:

- Normal: $\leq 7\%$ change from baseline
- Abnormal low decrease: Decrease of > 7 to $\leq 10\%$ from baseline
- Abnormal low increase: Increase of > 7 to $\leq 10\%$ from baseline
- Abnormal high decrease: Decrease of $> 10\%$ from baseline
- Abnormal high increase: Increase of $> 10\%$ from baseline

6.6.3.2 Continuous Descriptive Parameters

The following vital sign parameters will be summarized:

Table 6-9 Vital Sign Descriptive Parameters

Parameters		
Systolic blood pressure (mmHg)	Diastolic blood pressure (mmHg)	Pulse rate (bpm)
Respiratory rate (breaths/min)	Temperature (°C)	Weight (kg)
BMI (kg / m ²)	Waist Circumference (cm)	Hip Circumference (cm)
Waist-to-hip Ratio		

6.6.4 Electrocardiograms

6.6.4.1 QTc Derivation

QTc Bazett (QTcB) and QTc Fridericia (QTcF) are derived as follows:

Table 6-10 ECG PCS Criteria

Parameter	Derivation if RR available	Derivation if RR unavailable
QTcB	$\frac{QT}{\text{square root of } RR}$	$\frac{QT}{\text{square root of } 1/HR}$
QTcF	$\frac{QT}{\text{cubic root of } RR}$	$\frac{QT}{\text{cubic root of } 1/HR}$

QTcB = QTc Bazett; QTcF = QTcF Fridericia.

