2.2 List of Figures

No table of figures entries found.

3. List of Abbreviations and Definition of Terms

Table 3-1 Abbreviations and Definitions of Terms

Abbreviation/Term	Definition
AE	adverse event
AESI	adverse event(s) of special interest
ALP	alkaline phosphatase
ALT	alanine aminotransferase
APRI	aspartate aminotransferase to platelet count ratio index
AST	aspartate aminotransferase
ANCOVA	analysis of covariance
ATC	Anatomical Therapeutic Chemical
BMI	body mass index
CFB	change from baseline
CI	confidence interval
CMH	Cochran-Mantel-Haenszel
CRN	Clinical Research Network
CVC	cenicriviroc mesylate
DSMB	Data and Safety Monitoring Board
DILI	drug-induced liver injury
eCRF	electronic case report form
ECG	Electrocardiogram
ELF	Enhanced Liver Fibrosis
FIB-4	noninvasive hepatic fibrosis index score combining standard biochemical values (platelets, ALT, AST) and age
FWER	familywise error rate
GLP-1	glucagon-like peptide 1
HbA1c	hemoglobin A1c
HBcAb	hepatitis B core antibody
HBsAb	hepatitis B surface antibody
HBsAg	hepatitis B surface antigen
HCV	hepatitis C virus
HCVAb	hepatitis C virus antibody
HR	Heart rate
HR	hazard ratio
IgG	immunoglobulin G
IL	Interleukin
INR	international normalized ratio
ITT	intent-to-treat
LDH	lactate dehydrogenase
LDL	low-density lipoprotein
LS	least squares
MACE	major adverse cardiovascular events
MAR	Missing at random
MedDRA	Medication Dictionary for Regulatory Activities
MELD	Model of end stage liver disease
MNAR	Missing not at random

Abbreviation/Term	Definition
mITT	modified intent-to-treat
NAS	NAFLD activity score
NASH	nonalcoholic steatohepatitis
NCI CTCAE	National Cancer Institute Common Terminology Criteria for Adverse Events
NFS	NAFLD fibrosis score
OR	odds ratio
PCS	potentially clinically significant
PD	pharmacodynamics(s)
PK	pharmacokinetic(s)
PK/PD	pharmacokinetic/pharmacodynamic
PID	participant identification
PMM	pattern-mixture model
PP	per-protocol
[REDACTED]	
PT	preferred term
QT	time between the start of the Q wave and the end of the T wave (ECG)
QTc	QT interval corrected for heart rate
QTcB	QT interval corrected for heart rate using the Bazett formula ($QTcB = QT/(RR)^{1/2}$)
QTcF	QT interval corrected for heart rate using the Fridericia formula ($QTcF = QT/(RR)^{1/3}$)
SAE	serious adverse event
SAP	statistical analysis plan
[REDACTED]	
SI	Le Système International d'Unités (International System of Units)
SMQ	Standard MedDRA query
SOC	system organ class
T2DM	type 2 diabetes mellitus
TE	transient elastography

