5.1.1.4.5 Electrocardiograms

Electrocardiograms (ECGs) will be summarized by treatment group and in total for the Safety Population as follows:

Table 5-22 ECG Summaries

Type of Endpoint	Description	Timing	Methodology
ECG parameter values over time	Summary by parameter and analysis visit 
 Parameters specified in Section 6.6.4.3 	Part 1: Baseline, Treatment Period: Month 12 Part 2: (subjects newly randomized): Baseline, Treatment Period: Month 12 Part 2 (all subjects –continuing from Part 1 and newly randomized in Part 2): Through to Month 60 Biopsy, and Post biopsy ¹	CFB descriptive statistics

¹ Based on nominal visits defined in the schedule of assessments.

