6.6.4.2 Potentially Clinically Significant Criteria

Any abnormal findings that are considered clinically significant in the opinion of the investigator will be recorded as AEs or be captured as medical history, if already present at Screening. ECG results will be reviewed for clinically notable abnormalities according to predefined criteria. Subjects exhibiting Grade 3 or 4 PR or QT interval corrected for heart rate (QTc) interval will be summarized. Abnormalities in Fridericia's corrected QT interval (QTcF) interval, Bazett's corrected QT interval (QTcB) interval, QRS, PR, and heart rate (HR) will be summarized.

ECG results will be reviewed for clinically notable abnormalities according to the criteria described below.

For values of QTc, the categories are:

- Normal: Less than 450 msec
- Borderline: At least 450 msec and up to 480 msec

- Prolonged: More than 480 msec and up 500 msec
- Pathologically prolonged: More than 500 msec

For QTc change from baseline, the categories are:

- Normal: Decrease/no change/increase up to 30 msec
- Abnormal: Increase of more than 30 msec up to 60 msec
- Abnormal high: Increase of more than 60 msec

For QRS, the categories are:

- Abnormal low: Up to 50 msec
- Normal: More than 50 msec and less than 120 msec
- Abnormal high: At least 120 msec

For PR, the categories are:

- Normal: Less than 210 msec
- Abnormal: At least 210 msec

For HR, the categories are:

- Abnormally low HR: ≤ 50 bpm
- Normal HR: > 50 bpm and < 120 bpm
- Abnormally high HR: ≥ 120 bpm

Abnormalities are the last three categories listed for QTc, the last two for QTc change from baseline, the first and last for QRS, the last for PR and the first and last for HR.

In addition, Grade 3 or 4 QT interval corrected for heart rate (QTc interval) will be derived based on the ECG data and following the NCI CTCCAE definition.

- For QT, Grade 3 is defined as $QTc \geq 501$ msec on at least 2 separate ECGs and Grade 4 is defined as $QTc \geq 501$ msec or > 60 ms change from baseline and Torsade de pointes or polymorphic ventricular tachycardia or signs/symptoms of serious arrhythmia.

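### The SAP's QTc fallback for ECGs without RR omits the factor 60, so QTcB comes out 7.75 times and QTcF 3.91 times too large

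*SAP*

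**What the plan says.** Table 6-10 in SAP section 6.6.4.1 has two columns. With RR available, QTcB is QT over the square root of RR, and QTcF is QT over the cube root of RR. With RR unavailable, the divisors become the "square root of } 1/HR" and the "cubic root of } 1/HR". The table states no units. The abbreviation list (SAP Table 3-1) gives the same Bazett form: "QT interval corrected for heart rate using the Bazett formula ($QTcB = QT/(RR)^{1/2".

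Units come from section 6.6.4.2. Heart rate is in beats per minute ("Abnormally low HR: ≤ 50 bpm") and QTc is in msec, with limits at 450, 480 and 500. The top value category is "Pathologically prolonged: More than 500 msec". Change from baseline is also classified in msec, the lowest category being "Normal: Decrease/no change/increase up to 30 msec". Grade 3 requires a QTc of at least 501 "msec on at least 2 separate ECGs and Grade 4 is defined as" the same threshold, or a change above 60 ms, together with an arrhythmia finding.

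QTcB and QTcF are also summarized by visit, with change from baseline (Table 5-22, "ECG parameter values over time", and Table 6-11).

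**The concern.** The two columns should give the same QTc for the same ECG. They do so only if the fallback divisor is RR in the unit used by the first column. With heart rate in bpm, 1/HR is RR in minutes, while the msec limits require seconds.

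If the table is programmed as written, four things follow for ECGs without RR:

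- A single such ECG falls in the top QTc category, and two in one subject meet the derived Grade 3 rule. Grade 4 is less exposed because it also needs an arrhythmia finding.
- If RR is missing at only one of baseline and follow-up, the change from baseline is invalid. A fallback baseline gives a large false decrease, which the SAP classes as normal and which could hide a real prolongation.
- If RR is missing at both visits, a true change is multiplied by 7.75 or 3.91.
- By-visit means and mean changes shift in proportion to the share of ECGs without RR. A false difference between arms would appear if that share differed by arm, though the documents give no reason to expect this in a blinded trial.

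**Working it through.** The plan gives no numerical QTc result to reproduce, so the check compares its two formulas.

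**Inputs.** The fallback divisors and the RR formulas come from SAP Table 6-10. Heart rate in bpm and the 450, 480 and 500 msec limits come from SAP 6.6.4.2. The unit of RR is not stated.

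**Step 1: which RR unit fits the limits?** Take QT 400 msec and HR 60 bpm.

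- RR in seconds = 60/60 = 1. QTcB = QTcF = 400 msec, on the scale of the limits.
- RR in msec = 1000. QTcB = 400/√1000 = 12.6 and QTcF = 400/1000^(1/3) = 40.0, which the limits cannot classify sensibly.
- RR in minutes = 1/60. QTcB = 400 × √60 = 3098 and QTcF = 400 × 60^(1/3) = 1566. The columns agree, but both are off the scale of the limits.

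Only seconds fits, so RR = 60/HR with HR in bpm.

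**Step 2: ratio of the fallback to the RR formula.**

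- QTcB: √[(60/HR)/(1/HR)] = √60 = 7.746
- QTcF: [(60/HR)/(1/HR)]^(1/3) = 60^(1/3) = 3.915

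Neither ratio depends on HR or QT.

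**Step 3: one ECG, QT 400 msec at 75 bpm.**

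| | With RR = 60/75 = 0.8 s | Fallback as written | Difference |
|---|---|---|---|
| QTcB | 400/√0.8 = 447.2 | 400 × √75 = 3464.1 | 3016.9 |
| QTcF | 400/0.8^(1/3) = 430.9 | 400 × 75^(1/3) = 1686.9 | 1256.0 |

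**Step 4: QT above which the fallback exceeds 500 msec.** For QTcB this is 500/√HR, and for QTcF 500/HR^(1/3). Over the SAP's normal heart-rate range:

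- HR 51: 70.0 msec (QTcB) and 134.8 msec (QTcF)
- HR 119: 45.8 msec (QTcB) and 101.7 msec (QTcF)

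The QT values used here, 300 to 400 msec, lie far above these thresholds.

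**Step 5: change from baseline.** At QT 400 msec and 75 bpm with no true change, a baseline with RR and a follow-up without it give a QTcF change of +1256 msec. The reverse gives −1256 msec. With RR missing at both visits, the 30 msec limit is crossed by a true rise of 30/3.915 = 7.7 msec (QTcF) or 30/7.746 = 3.9 msec (QTcB).

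**Step 6: shift in a visit mean.** The shift is the share without RR times the difference in step 3. The share is an assumption, since the documents do not give it. At 0% there is no shift; at 0.1% it is +1.3 (QTcF) and +3.0 msec (QTcB); at 1%, +12.6 and +30.2; at 10%, +125.6 and +301.7.

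**The case against.** The strongest objection is that the table states no units in either column. RR = 1/HR is true in coherent units, so with heart rate in beats per second both columns would be right. On this view the defect is missing units rather than a missing 60, and it is uneven to read RR generously as seconds while reading HR literally as bpm. The lack of units is real, and the fix should supply them. The rest does not stand: bpm is the only heart-rate unit in the SAP, nothing supports beats per second, and seconds is the only RR unit compatible with the msec limits.

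The other objections concern weight. No document says that any ECG lacks RR. Values such as 3464 msec are impossible on sight, and the SAP provides for review of ECG results and for data listings. The table and dataset specifications are separate documents, which may already contain 60/HR. Safety analyses are mainly descriptive, with no prespecified hypotheses (SAP 5.1.1.4), and the adverse events of special interest are liver biochemistry elevations, not QTc. All of this limits the consequence, and undetected carry-through to the report is not the likely outcome. It does not correct the SAP. The SAP presents itself as the technical specification, its text goes into the study report (section 5.1), and a programmer who repairs the formula silently departs from it.

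**Conclusion.** The concern holds. The fallback in Table 6-10 gives a wrong result when followed: QTcB is too large by a factor of 7.75 and QTcF by 3.91. No other part of either document corrects it, including the SAP's sections on changes to analyses and its summary of changes.

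The conclusion rests on heart rate being in bpm, which the SAP states, and RR being in seconds, which follows from the msec limits. The effect is confined to ECGs without RR, so its size in the trial cannot be determined from the documents and could be nil. Uncorrected QT, heart rate, ECGs with RR, investigator-reported ECG adverse events and all efficacy analyses are unaffected. It should be corrected, but it does not threaten the trial's main conclusions.

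**What to change.** Before database lock, write the fallback as QTcB = QT/√(60/HR) and QTcF = QT/(60/HR)^(1/3). Add a footnote to Table 6-10 giving QT in msec, HR in bpm and RR in seconds. The two columns then agree exactly; at QT 400 msec and 75 bpm both give 447.2 (QTcB) and 430.9 (QTcF). Check that the dataset and table specifications use the same form. The cost is a one-line SAP correction and a footnote, with no change to data collection.

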6.6.4.2 Potentially Clinically Significant Criteria

Any abnormal findings that are considered clinically significant in the opinion of the investigator will be recorded as AEs or be captured as medical history, if already present at Screening. ECG results will be reviewed for clinically notable abnormalities according to predefined criteria. Subjects exhibiting Grade 3 or 4 PR or QT interval corrected for heart rate (QTc) interval will be summarized. Abnormalities in Fridericia's corrected QT interval (QTcF) interval, Bazett's corrected QT interval (QTcB) interval, QRS, PR, and heart rate (HR) will be summarized.

ECG results will be reviewed for clinically notable abnormalities according to the criteria described below.

For values of QTc, the categories are:

- Normal: Less than 450 msec
- Borderline: At least 450 msec and up to 480 msec

- Prolonged: More than 480 msec and up 500 msec
- Pathologically prolonged: More than 500 msec

For QTc change from baseline, the categories are:

- Normal: Decrease/no change/increase up to 30 msec
- Abnormal: Increase of more than 30 msec up to 60 msec
- Abnormal high: Increase of more than 60 msec

For QRS, the categories are:

- Abnormal low: Up to 50 msec
- Normal: More than 50 msec and less than 120 msec
- Abnormal high: At least 120 msec

For PR, the categories are:

- Normal: Less than 210 msec
- Abnormal: At least 210 msec

For HR, the categories are:

- Abnormally low HR: ≤ 50 bpm
- Normal HR: > 50 bpm and < 120 bpm
- Abnormally high HR: ≥ 120 bpm

Abnormalities are the last three categories listed for QTc, the last two for QTc change from baseline, the first and last for QRS, the last for PR and the first and last for HR.

In addition, Grade 3 or 4 QT interval corrected for heart rate (QTc interval) will be derived based on the ECG data and following the NCI CTCCAE definition.

- For QT, Grade 3 is defined as $QTc \geq 501$ msec on at least 2 separate ECGs and Grade 4 is defined as $QTc \geq 501$ msec or > 60 ms change from baseline and Torsade de pointes or polymorphic ventricular tachycardia or signs/symptoms of serious arrhythmia.

6.6.4.3 Continuous Descriptive Parameters

The following ECG parameters will be summarized:

Table 6-11 ECG Descriptive Parameters

Parameters		
Heart rate	QRS interval	QT interval
	PR interval	QTcB
		QTcF

QTcB = QTc Bazett; QTcF = QTc Fridericia.

- Section 4.1.1 Overall Design: clarified that the surrogate endpoint for Part 1 analyses are based on histopathological data for the endpoint, and that subjects who continue beyond Month 12 would continue on their same treatment arm throughout the rest of the study. In addition, updated the planned sample size in Part 1 to be approximately 1200
- Section 4.1.1 Part 2: rearranged sentences for clarity and consistency; updated Part 2 randomization information for change in stratification per protocol amendment 4
- Section 4.1.2 Number of Participants: clarified that the Part 1 analysis would commence after completion of the 12-month visit assessments (including biopsy)
- Section 4.2 Study Objectives and Endpoints: Objectives and endpoints were rearranged into global and EU-specific objectives and endpoints, as well as for Part 1 and Part 2 analyses, and endpoints were rephrased for clarity (e.g., summary measures were reworded to be endpoints).

- Section 4.3 Schedule of Assessments: updated to current version
- Section 5.1 Statistical Methods Planned in the Protocol and Determination of Sample Size: added sentence about a separate SAP for health economics and outcomes research analyses
- Section 5.1.1 Statistical and Analytical Plans: updated SAS version to be 9.4 or newer

- Section 5.1.1.1.4 Estimands: added estimand language for primary, key secondary, and secondary endpoints
- Section 5.1.1.1.5 Missing Data: separated the data methods for Part 1 analyses from the Part 2 analyses; updated the explanatory variables to include the ELF score at baseline and the weight change from baseline to Month 12
- Section 5.1.1.1.6 Site Pooling: added clarification regarding site as a stratification factor for specified Part 1 analyses
- Section 5.1.1.1.7 Other Common Conventions: clarified what the Part 1 analyses would summarize. Part 1 analyses will include efficacy analyses through Month 12 and available safety data through the Part 1 database lock for the Part 1 participants.
- Section 5.1.1.2.2 Participant Disposition: clarified that the disposition will include those who discontinued study drug early or discontinued from the study early for Part 1 or Part 2 of the study. Also, disposition will be presented by total population, treatment group, and by region, but not by study site.
- Section 5.1.1.2.3 Protocol Deviations: corrected language such that significant protocol deviations will be summarized for the ITT population
- Section 5.1.1.2.4 Demographics: removed “Other” for race; any categories for multiple races will be presented under its own multiple race category (e.g., a subject who is both “White” and “Asian” will be presented as “Multiple race: White, Asian”)
- Section 5.1.1.2.5 Baseline Characteristics: clarified fibrosis stage method to be NASH CRN fibrosis stage; clarified baseline definition to be last available assessment prior to study intervention administration; added other disease characteristics like glucagon-like peptide-1 analogue use, sodium-glucose cotransporter-2 inhibitor use, insulin use, categories for liver stiffness, CAP score, ELF score, and key laboratory values; removed others that were not collected in the study (Framingham score, smoking status)
- Section 5.1.1.2.6 Medical History: updated MedDRA version to 22.1 or newer
- Section 5.1.1.2.7 Prior and Concomitant Medications: clarified ATC drug class to be the 4th level, drug code and preferred drug name; clarified that prior and concomitant medications would be presented separately; removed “subsequent medications” parameter, as there will be no additional follow-up on medications after the follow-up visit

- Section 5.1.1.3 Efficacy Analyses: clarification added for the NASH CRN Staging System used for the endpoints; clarified that the Ishak scoring system used in the study is the “modified Ishak scoring system”; added ELF score under fibrosis indices; corrected SF-36 v2 scale names; removed Framingham score, which is not collected in the study; aligned language in SAP to that of the protocol (e.g., protocol used 6 months, SAP updated 180 days to be 6 months)
- Section 5.1.1.3.1 Endpoint Domain 1: Testing hierarchy added for the global analyses as well as region-specific Europe analyses; endpoints, descriptions, and methodologies were updated to reflect previous changes in the SAP amendment
- Section 5.1.1.3.3 Multiple Comparisons Procedure for Primary and Secondary Endpoints: clarified that the alpha control is over both Part 1 and Part 2 of the study with a familywise 0.00125 significance level
- Section 5.1.1.4 Safety Analyses: clarified what the safety endpoints are, along with what the applicable baseline definition was
- Section 5.1.1.4.2 Adverse Events: updated the MedDRA version to be v22.1 or newer; added “grade 2 or above” and “grade 3 or above” as TEAE categories to the overall AE summary table; added treatment-related TESAEs as a category to the overall AE summary table
- Section 5.1.1.4.3.1 Liver Biochemistry: updated section to encompass liver biochemistry elevations, not simply potential Hy’s Law or suspected drug-induced liver injuries
- Section 5.1.1.5 Subgroup Analyses: added subgroup analyses for NASH CRN fibrosis stage and T2DM for the key secondary endpoint and other secondary endpoints; clarified geographic region subgroups; removed “diabetic subjects” subset for the subgroup analyses for prior and concomitant medication use; added sodium-glucose cotransporter-2 (SGLT-2) inhibitor use and insulin use subgroups; added weight loss during the study at any time and also weight loss during the study at the liver biopsy assessment as subgroups; removed Framingham score and smoking status subgroup analyses; clarified that the length of biopsy subgroups would be based on both the baseline and Month 12 liver biopsy lengths; updated the alcohol use subgroup categories to be current drinker, former drinker, and non-drinker
- Section 5.1.1.6.1 Part 1 Analyses: clarified that the Part 1 analyses would occur when the approximately 1200 planned participants were followed through the Month 12 visit assessment; clarified that an unblinded team outside of the study team would be performing the unblinded activities through Part 2

- Section 5.2.1 Changes in the Conduct of the Study: approximately 1200 were planned but 1293 were randomized through the screening process during study execution. This would affect the numbers randomized through Part 2, but general conduct of the study is unaffected.

- Section 6.1 Study Treatment Conventions: clarified that the actual fibrosis stage and T2DM status collected via the electronic database would be used for analyses
- Section 6.2.2 Safety: clarified that plasma and serum samples collected beyond Visit 2 would still be analyzable for polymorphisms, genotype status, and pharmacogenetic biobanking
- Section 6.6.1.4 Major Adverse Cardiovascular Events (MACE): added section to describe how potential MACE cases would be identified in the AE dataset; 4-point MACE would be used, and MedDRA SMQs that would be used to identify cases were listed
- Section 6.6.1.5 Type 2 Diabetes Mellitus (T2DM): added section to describe how new onset T2DM cases would be identified in the AE dataset, along with the specific MedDRA preferred terms
- Section 6.6.2.2 Continuous Descriptive Parameters: added the ELF score and PRO-C3
- Section 6.6.3.1 Potentially Clinically Significant Criteria: added PCS criteria for weight change that include abnormal increases or abnormal decreases
- Section 7 References: 3 references added for the MACE criteria
- Section 8 Summary of SAP Changes: added
